In transplant patients, the use of post-surgical abdominal drains on a routine basis has shown an increase in total protein losses in patients with refractory ascites, an increase in ascending infections secondary to drainage, infection and pain at the insertion point of the drain, as well as as, an increase in hospital stay. Nor can a higher rate of postsurgical bleeding and bile leakage be ruled out in patients with abdominal drainage.

Currently, in the few studies that there are in reference to the systematic use of abdominal drains in ITH, the need for them prophylactically is being discussed as an early diagnosis of postoperative intra-abdominal complications is not observed, but complications are seen to increase secondary to drainage. Therefore, the need to use it systematically in all patients is currently under discussion.

Currently, we are facing an increase in ERAS® (Enhanced Recovery After Surgery) programs, which began in 2008 with colorectal surgery and are currently expanding to other surgical procedures. These programs advocate reducing the number of drains and even not using them in patients with a low risk of post-surgical complications.

In the current bibliography, the methodology of the studies is varied, with the majority being non-randomized retrospective studies, which is why it is a subject that requires studies with a better methodological design and a higher number of patients to obtain

conclusions of clinical relevance. that can set the direction in this area that is in constant discussion.

Given the absence of any randomized non-inferiority clinical trial that studies the routine use of abdominal drainage in the postoperative period of liver transplantation, we consider that it is necessary to carry it out to increase the evidence.

The number of HT performed in each center is limited and variable annually, which is why we consider that the best design for this clinical trial is a European multicenter.

- **OBJECTIVE AND PURPOSE OF THE TEST**

The objective of our randomized clinical trial is to evaluate whether the prophylactic use of intra-abdominal drains in LT patients reduces postoperative intra-abdominal complications, compared to their routine use.

- **Main goal.**
 - To assess whether the prophylactic use of abdominal drains in the postoperative period of LT increases the number of abdominal complications in the 90 postoperative days (Clavien-Dindo)
- **Secondary objectives.**

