The Principal Investigator will ensure that subject identification codes are kept for at least fifteen years after the trial has been completed or discontinued.

The data of all the CRDs will be entered into a database created for this purpose and equipped with safety margins and internal coherence standards. This database will be equipped with a double entry system and filters that prevent and detect any type of inconsistency or error in it. The information will be validated through internal consistency controls, studying the missing values. The data will be verified and corrected until the

database is fully validated. Once the database is purged, the variables will be recoded generating new variables (regrouping, sums, etc.).

- **Sample size.**

The hypothesis of this study was that the risk of postoperative complications at 90 days in the ND group would not be higher than in group D. A non-inferiority configuration was selected because the omission of drain placement is advantageous in terms of relieving to patients from discomfort and a decrease in medical cost. In calculating the sample size, the risk of an early postoperative complication related to LT was assumed to be 9% in the drain group and 6% in the no-drain group according to the literature review performed. Under a 4% non-inferiority margin, an alpha error of 0.05, and a statistical power of 80%, the sample was calculated as 174 patients in each arm. Assuming a 5% dropout rate, a total of 365 patients will be recruited into this study.

- **Statistic analysis**

The subsequent statistical analysis will be performed with the SPSS v.25 software.

- **Descriptive analysis.**

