The demographic data and other baseline characteristics of the trial subjects will be described using descriptive statistical indices, for the overall number of patients and for each of the groups of patients under study. Continuous variables will be described using measures of central tendency (mean) and measures of dispersion (standard deviation). While the categorical variables will be described through absolute and relative frequency tables. The baseline characteristics shown by the groups of participants included in the study will be compared. Statistical tests will be performed depending on the nature of the variables. To study the relationships between variables, standard chi-square tests have been used in the case of qualitative variables and Pearson's correlation in the case of quantitative variables. In each situation, any association in which the p-value was less than 0.05 was considered statistically significant. The magnitude of the association between qualitative variables will be made by calculating the relative risk, and between quantitative

variables using Pearson's correlation coefficient. In this multivariate analysis, the odds ratios will be obtained with a 95% confidence interval.

- **Analysis of the main variable**

The primary efficacy criterion is the comparison of the incidence of postsurgical complications according to the Clavien-Dindo classification.

- **Secondary variables analysis**

The univariate and multivariate study of all the included variables will be carried out.

- **ETHICS**

This study will be carried out in European hospitals in accordance with current European legislation that regulates the performance of clinical trials, for which this protocol is established as a reference document for review by the Ethics Committees, as well as for the taking of practical decisions in the management of included patients by participating investigators. The study will only begin after obtaining written authorization from the Clinical Research Ethics Committee.

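### The trial is sized for non-inferiority with a 4% margin, but no primary analysis tests the result against that margin

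*Combined protocol and SAP*

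**What the plan says.** **Design.** Statistics, Sample size, says: "A non-inferiority configuration was selected because the omission of drain placement is advantageous". The hypothesis is that the 90-day complication risk without a drain (ND) is no higher than with one (D). The assumed risks are 9% in D and 6% in ND. The planning parameters are: "Under a 4% non-inferiority margin, an alpha error of 0.05, and a statistical power of 80" percent. The result is 174 per arm, or 365 in total with 5% dropout.

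**Primary analysis.** Statistics, Analysis of the main variable, consists of one sentence: "The primary efficacy criterion is the comparison of the incidence of postsurgical complications according to the Clavien-Dindo classification".

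**Other inferential text.** This sits under Descriptive analysis and is not assigned to the primary outcome:
- test: "standard chi-square tests have been used in the case of qualitative variables"
- significance: "any association in which the p-value was less than 0.05 was considered statistically significant"
- effect measure: "The magnitude of the association between qualitative variables will be made by calculating the relative risk"
- the only confidence interval, for a multivariate analysis: "the odds ratios will be obtained with a 95% confidence interval"

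**Objective.** The Main goal is worded as a question about a difference, not about non-inferiority: "To assess whether the prophylactic use of abdominal drains in the postoperative period of LT increases the number of abdominal complications".

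No section states whether the 4% is absolute or relative, or whether the alpha of 0.05 is one- or two-sided.

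**The concern.** A non-inferiority trial is decided by comparing a confidence limit for the treatment difference with the margin. Here the margin sets the sample size and is then not used again. A reader looking for an analysis of the primary outcome finds only the general rule for qualitative variables: chi-square, p<0.05, relative risk. That rule asks whether the two risks are equal, on a ratio scale, while the sample size rests on an absolute difference.

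Two things are at stake. First, a non-significant chi-square could be taken as evidence that omitting the drain is safe, on data that fail the trial's own criterion. The plan does not say it will be read that way, but its analysis text does not prevent it. Second, with the confidence level unwritten, the same data can pass at one level and fail at another. The trial is unmasked, so that choice should not remain open once results can be seen.

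**Working it through.** **Inputs (Sample size section).** Risk 0.09 in D and 0.06 in ND, margin 0.04, alpha 0.05, power 80%, 174 per arm.

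**1. Reproducing the planned size.** Take the margin as an absolute risk difference with unpooled variance:

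n per arm = (z_α + z_β)² × [0.09×0.91 + 0.06×0.94] / (0.04 + 0.03)²

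The variance term is 0.0819 + 0.0564 = 0.1383, and the denominator is 0.07² = 0.0049.
- One-sided 0.05: (1.645 + 0.842)² × 0.1383 / 0.0049 = 174.5.
- Two-sided 0.05 (one-sided 0.025): (1.960 + 0.842)² × 0.1383 / 0.0049 = 221.5.
- A margin of 4% on the relative scale, at one-sided 0.05, would need about 757 to 806 per arm, depending on the formula.

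Dropout: 348 × 1.05 = 365.4, which agrees with 365. Among these options, 174 fits an absolute 4-point margin at one-sided 0.05, that is, a two-sided 90% interval. The size itself is sound.

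**2. The chi-square p-value does not track the margin.** Take 174 per arm and 16 events in D (9.2%). The Newcombe upper bound for ND minus D is the observed difference plus √[(U_ND − p_ND)² + (p_D − L_D)²], where U and L are Wilson limits.
- 16 v 10, 90% level: −0.0345 + √[(0.0938 − 0.0575)² + (0.0920 − 0.0619)²] = +0.013.
- 16 v 24, 90% level: +0.0460 + √[(0.1865 − 0.1379)² + (0.0920 − 0.0619)²] = +0.103.

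| D v ND events | chi-square p | 90% upper bound | 95% upper bound | below +0.04? |
|---|---|---|---|---|
| 16 v 10 | 0.22 | +0.013 | +0.022 | yes at both levels |
| 16 v 13 | 0.56 | +0.033 | +0.043 | 90% only |
| 16 v 16 | 1.00 | +0.052 | +0.063 | no |
| 16 v 24 | 0.18 | +0.103 | +0.114 | no |

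The chi-square is non-significant for every ND count from 7 to 28. The margin is met only up to 14 events (90% interval) or 12 events (95% interval).

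**3. Operating characteristics.** Exact binomial enumeration, 174 per arm, chi-square without continuity correction:

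| True risk, D v ND | chi-square p>0.05 | 90% Newcombe rule passes | 95% Newcombe rule passes |
|---|---|---|---|
| 9% v 6% (planned) | 81.5% | 79.3% | 67.9% |
| 9% v 13% (4 points worse) | 77.4% | 4.9% | 2.4% |
| 9% v 15% (6 points worse) | 58.7% | 1.3% | 0.5% |

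Under the planned risks, 61% of trials are non-significant and meet the margin (90% Newcombe), and 20.5% are non-significant and miss it. In 11.4% of trials the result passes at 90% and fails at 95%. With a Wald interval, power is 81.0% (90%) and 71.2% (95%).

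**The case against.** The strongest reply is that the Sample size section, under the same Statistics heading, already states the non-inferiority design, the margin and the direction of the hypothesis. A competent analyst would apply them. The scale and sidedness can be worked back from 174 per arm. The chi-square sits under Descriptive analysis and is never assigned to the primary outcome, so the 77% and 59% figures price a misreading and are not error rates of the written plan.

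Part of this stands. Those two figures are conditional, and the point does not depend on them: the comparison of 16 v 10 with 16 v 24 holds without any misreading. The intended scale and level can be inferred, but inference from a sample size is not a pre-specified rule. The only confidence level the plan prints, 95%, differs from the 90% that the sample size supports.

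Two further objections bear on the remedy. Newcombe is one acceptable interval among several; at 174 per arm it gives 79.3% power and first reaches 80% at 180 per arm, whereas Wald gives 81.0%. Also, the binary endpoint (which complications, what grade, the start of the 90 days) and the analysis population are not settled in the documents. These are separate gaps, but the rule below cannot be applied until they are closed.

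**Conclusion.** The concern holds and must be fixed before analysis. The trial's central conclusion depends on a margin that no analysis uses, and the only general rule offered answers a different question. At 174 per arm, chi-square p-values of 0.22 and 0.18 fall on opposite sides of the margin, and two arms with an identical 16 events (p=1.00) do not show non-inferiority. If non-significance were taken as not worse, that conclusion would follow in 77% of trials with a true 4-point excess, against 4.9% under the 90% interval rule. Leaving the level open changes the outcome in 11.4% of trials under the planned risks.

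These figures assume the plan's 9% risk in the drain arm, 174 analysed per arm, a binary outcome per patient, and an absolute 4-point margin. The sample size calculation is not in error.

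**What to change.** Replace the sentence under Analysis of the main variable with a full specification:
- **Estimand and measure:** risk difference, ND minus D, in the proportion of patients with at least one primary-endpoint complication by day 90, with D as reference. The endpoint and analysis population should be defined alongside it.
- **Interval:** one named method. Newcombe is suggested; it is closed-form, so it can be computed even if SPSS v.25 does not produce it.
- **Decision rule:** non-inferiority only if the upper bound is below +4 percentage points. The sponsor should confirm that the 4% is an absolute difference.
- **Confidence level, stated in advance:** a two-sided 90% interval (one-sided alpha 0.05) matches 174 per arm.
- **Order:** test superiority only after non-inferiority is met. Keep the relative risk and odds ratio as descriptive.
- **Main goal:** reword it as the same non-inferiority statement.

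**Cost.** With the 90% interval, wording only and no extra patients, accepting power of about 79% (Newcombe) or 81% (Wald). A strict 80% with Newcombe needs 180 per arm (360 × 1.05 = 378 recruited). With a two-sided 95% interval there are two options: keep the size and restate power as about 68% (Newcombe) to 71% (Wald), or raise it to about 222 per arm by the standard formula (444 / 0.95 = 467.4, about 468 recruited). Newcombe needs about 227 per arm for 80% power at that level.

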 - To evaluate the possible improvement in the quality of life of the transplanted patient derived from the absence of postsurgical drainage (SF-36).
 - Evaluate the postoperative stay in both groups.

- **STUDY DESIGN**

Unmasked European multicenter randomized clinical trial with two arms parallel to the study.

Patients who meet the inclusion criteria will be offered to participate in this study by signing an informed consent. An informed consent approved by the Research Ethics Committee of the Virgen de la Arrixaca University Hospital will be used.

Patients who give their consent for the study will be randomized to the drainage group (D) and the control group without drainage (ND) before the beginning of the abdominal wall closure.

In the drainage group (D), it will be placed on the right flank / right iliac fossa. The drain will be connected to a bag and fixed to the skin with a silk. Said drain will be placed at the level of the surgical bed.

Regarding the control group, intraoperative drainage will not be placed, except when the surgeon's discretion considers it necessary due to the high risk of bleeding, bile leakage or any other process / complication in which it may benefit from intra-abdominal drainage.

All patients, regardless of the randomization group, will receive a quality of life questionnaire (SF-36) prior to surgery that they must complete.

All patients will receive routine antibiotic prophylaxis 60 minutes before surgery, repeating the number of doses that are required according to blood loss and surgical time. Antibiotic prophylaxis will be adjusted according to the resistance protocols of each participating center.

○ **DATA COLLECT**

The following variables will be collected for each patient:

- **Recipient preoperative** variables: gender, age, pre-transplant stay, BMI, ASA, diabetes, HTN, dialysis, MELD, Child-Pugh, serology, albumin, bilirubin, INR, CRP, creatinine, ascites, SBP, prothrombin time, encephalopathy, time from SSI to HT (months), retransplantation, previous surgeries, cirrhosis etiology, indication for transplantation, sarcopenia.
- **Donor** characteristic variables: age, stay in ICU, vasoactive drugs, cultures, antibiotics, CIT, WIT, type of donation (DBD / DCD), previous immunosuppression.

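### The two secondary objectives, SF-36 and postoperative stay, have no defined between-arm estimate; the pre-transplant SF-36 has no role, and 16 SF-36 comparisons share one unadjusted p<0.05 rule

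*Combined protocol and SAP*

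**What the plan says.** Under Secondary objectives the protocol lists two aims: a possible gain in SF-36 quality of life from leaving out the drain, and "Evaluate the postoperative stay in both groups". Study variables lists eight SF-36 domains, recorded at waiting-list inclusion and at one and four months after surgery.

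The whole text under Secondary variables analysis is "The univariate and multivariate study of all the included variables will be carried out".

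The general rules are in the paragraph headed Descriptive analysis:

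- Choice of test: "Statistical tests will be performed depending on the nature of the variables".
- Two qualitative variables: chi-square, and "The magnitude of the association between qualitative variables will be made by calculating the relative risk".
- Two quantitative variables: "Pearson's correlation in the case of quantitative variables".
- Multivariate work: "In this multivariate analysis, the odds ratios will be obtained with a 95% confidence interval".
- Significance: "any association in which the p-value was less than 0.05 was considered statistically significant".

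The same paragraph says that continuous variables are described by mean and standard deviation, and that indices are given overall and by group. It opens on demographic and baseline data.

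**The concern.** Randomised arm is a two-level variable, while an SF-36 score and a number of days are quantitative. None of the named methods is assigned to that pairing. The plan therefore does not say what number will answer either secondary objective.

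Three choices stay open until the data have been seen:

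- **Baseline SF-36.** Scores could be compared raw, as change from baseline, or adjusted for baseline. These differ in precision.
- **Which SF-36 result counts.** No domain or time is singled out, and there is no multiplicity rule. The trial is unmasked and the SF-36 is patient-reported, so a free choice of domain and time would be hard to defend.
- **Stay when a patient dies in hospital.** No rule is given, although 90-day mortality is recorded.

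A lesser gap is that the sentence on all included variables does not keep variables arising after randomisation out of a model for the drain effect. The variable lists include hospital stay, graft function and post-transplant antibiotics.

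**Working it through.** **Coverage of the named methods**

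| Method in the Statistics section | Pairing it serves | Gives a difference in points or days? |
|---|---|---|
| Chi-square, relative risk | qualitative with qualitative | No |
| Pearson's correlation | quantitative with quantitative | No |
| Odds ratio with 95% CI | binary outcome | No |
| Test chosen by type of variable | any | A p-value only |
| Mean and SD by group | paragraph opening on baseline data | Not a stated comparison |

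**Sample size, used here only as an input.** The plan states 174 per arm for the primary comparison (9% v 6%, margin 4%, alpha 0.05, power 80%). With one-sided alpha, (0.09×0.91 + 0.06×0.94) × (1.645 + 0.842)² / 0.07² = 174.5, which reproduces it. No precision is stated for SF-36 or stay.

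**SF-36 precision.** The 95% CI half-width for a mean difference, in SD units, is t(346) × √(2/174) = 1.967 × 0.1072 = 0.211. Multiply by √(1−r²) with baseline as covariate, or by √(2(1−r)) for a change score. The documents give no correlation r, so r is an assumption.

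| Assumed r | Unadjusted | Baseline as covariate | Change score |
|---|---|---|---|
| 0.1 | 0.211 | 0.210 | 0.283 |
| 0.3 | 0.211 | 0.201 | 0.250 |
| 0.5 | 0.211 | 0.183 | 0.211 |

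Below r = 0.5 a change score is less precise than ignoring baseline. Covariate adjustment does not lose to either alternative in this range. These figures assume 174 analysed per arm; missing questionnaires would widen all of them.

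**Multiplicity.** There are 8 domains × 2 times = 16 comparisons. If independent, 1 − 0.95¹⁶ = 0.560. For equally correlated normal test statistics, numerical integration gives 0.476, 0.374 and 0.264 at assumed correlations of 0.3, 0.5 and 0.7.

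**Stay and in-hospital death.** All inputs are assumed: log-normal stay with median 15 days under drain, 10% shorter without, log-SD 0.5 or 0.8, not capped at 90 days. The mean is 15 × exp(SD²/2), that is 17.00 v 15.30 days at log-SD 0.5 and 20.66 v 18.59 at 0.8. For the median with deaths ranked longest, each arm's value is the 0.5/(1 − death proportion) quantile of stay in survivors. The table shows no drain minus drain, in days, as log-SD 0.5 / 0.8.

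| In-hospital deaths, drain v no drain | Mean, survivors | Mean, death counted as 90 days | Median, deaths ranked longest |
|---|---|---|---|
| 5% v 5% | −1.70 / −2.07 | −1.61 / −1.96 | −1.55 / −1.58 |
| 3% v 6% | −1.70 / −2.07 | +0.59 / +0.14 | −1.24 / −1.08 |

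For example, at log-SD 0.5 with unequal deaths: (0.94 × 15.30 + 0.06 × 90) − (0.97 × 17.00 + 0.03 × 90) = 19.78 − 19.19 = +0.59.

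**When the first SF-36 is completed.** Study design and Follow-up place it before the operation. The randomisation section places it at first contact at recruitment. Description of the intervention and Study variables place it at waiting-list inclusion. The time between these may be long, which bears on r.

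**The case against.** **The paragraph already gives mean and SD by group.** Read generously, this extends beyond baseline data, and a difference with CI can be derived from it. The choice of test by type of variable may also imply a t-test or rank test. That reading is possible, but it fixes no effect measure, no baseline role and no death rule, so the gap remains.

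**A reader might infer that the death rule reverses the stay result.** The documents do not support that as a general statement. In the table the sign changes only when no-drain deaths are about double and death is coded as 90 days, a coding that the protocol nowhere suggests. With 3% deaths under drain, no-drain deaths must exceed about 5.2% (log-SD 0.5) or 5.8% (0.8). With equal deaths the rule matters little.

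**A reader might infer that the plan will adjust the drain effect for stay or other postoperative variables, or enter every listed variable in one model.** The text states no such plan. A screened risk-factor model of pre-randomisation variables is a common reading and would do little harm. What stands is a missing safeguard.

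**The 56% figure is high.** SF-36 domains are correlated, so independence overstates the risk; the 26% to 48% range is the fairer one, under assumed correlations.

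**The yield is modest.** This stands too: the precision gain is negligible at r of about 0.1, and several summaries of stay would be acceptable.

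**Conclusion.** The concern holds in limited form and should be corrected. Neither secondary objective has a defined between-arm estimate, the pre-transplant SF-36 has no role, and p<0.05 applies without restriction to 16 SF-36 comparisons.

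That the estimates are undefined follows from the text alone. The sizes rest on assumptions. At r = 0.3 the CI half-width runs from 0.201 to 0.250 SD depending on how baseline is used. The chance of at least one false-positive SF-36 result is 26% to 48% at correlations of 0.7 to 0.3, and 56% under independence. For stay, the death rule matters mainly if deaths differ between arms. The finding does not touch the primary comparison.

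**What to change.** Replace the sentence under Secondary variables analysis with the following.

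1. **SF-36.** For each domain, report the difference between randomised arms at one and four months with 95% CI, adjusted for the pre-transplant score of that domain (ANCOVA or a mixed model), not as a change score. First reconcile when that score is taken. State how deaths are handled so that the estimand matches the model: a likelihood-based mixed model that treats deaths as missing data does not estimate the difference among survivors. Report deaths and missing questionnaires by arm. Name one key domain and time before outcome data are analysed; report the other 15 results as estimates with CIs and no claim of significance.
2. **Stay.** Report the difference between randomised arms in days with 95% CI under one death rule fixed in advance, for example the median with in-hospital deaths ranked longest. Show deaths by arm beside it.
3. **Modelling.** Any model that estimates the drain effect uses arm as randomised and only pre-randomisation covariates. Label other multivariate modelling exploratory.

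The cost is wording, one early choice of key domain and time, and slightly more analysis; no new data are needed. The SF-36 gain may be small. The stay estimate will be imprecise: under the assumptions above, the bootstrap half-width for the median difference was about 2.1 to 3.6 days, so the result will be descriptive rather than decisive.

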Randomization: 2 groups of equal size, total n = 365 patients. Simple intraoperative randomization prior to closure of the abdominal wall after fulfilling all the inclusion criteria and none of the exclusion criteria.

Masking: no masking.

Study population: liver transplants for all etiologies.

Variables analyzed:

- **Recipient preoperative** variables: gender, age, pre-transplant stay, BMI, ASA, diabetes, HTN, dialysis, MELD, Child-Pugh, serology, albumin, bilirubin, INR, CRP, creatinine, ascites, SBP, prothrombin time, encephalopathy, time from SSI to LT (months), retransplantation, previous surgeries, cirrhosis etiology, indication for transplantation, sarcopenia.
- **Donor** characteristic variables: age, stay in ICU, vasoactive drugs, cultures, antibiotics, CIT, WIT, type of donation (DBD / DCD), previous immunosuppression.
- **Intraoperative** variables: placement or not of abdominal drainage, surgical time (min), transfusions, blood loss, surgical technique, arterial anastomosis type, biliary anastomosis type, donation with extended criteria, recipient with extended criteria, clamping times.
- **Postoperative** variables: ICU stay, hospital stay, abdominal complications (collection, bile leak, hematoma, hemorrhage, paralytic ileus, ascites, bleeding, wound drainage complications, vascular anastomosis complications, mechanical obstruction, hollow viscus perforations, wound complications surgery), graft function, post-transplant antibiotic therapy, post-transplant immunosuppressive regimen, number of post-LT HC, mortality at 90 days, global complications at 90 days.
- **SF-36:** Physical function, physical role, body pain, general health, vitality, social function, emotional role, mental health (on inclusion in the waiting list, one month after surgery, 4 months after surgery).

● INDEX	Page
○ Summary	3
○ Index	5
○ List of acronyms and definition of terms	6
○ General Information	7
○ Justification	10
○ Objective and purpose of the study	11
○ Study design	11
○ Study population	14
○ Treatment of subjects	15
○ Study variables	17
○ Follow-up of subjects	17
○ Safety assessment	17
○ Statistics	18
○ Ethics	20
○ Informed Consent	21
○ Direct access to source data / documents	21
○ Data management and record file.....	21
○ Data protection	22
○ Financing and insurance	22
○ Publication policy	22
○ Bibliography	23
○ Annexes	25

LIST OF ACRONYMS AND DEFINITION OF TERMS

- **ASA:** American Society of Anesthesiologists Classification
- **BMI:** Body Mass Index

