Investigational products will be supplied by the hospital. Said product will be administered intraoperatively and supplied to the surgical ward when its placement is confirmed depending on the group assigned after randomization.

- **Previous and concomitant treatments.**

Any pharmacological treatment carried out during the experimental period must be registered in the CRD. The principal investigator of the study will judge the suitability of the participant's continuity in the study.

The taking of drugs or other treatments that may modify the biological effects of the products under investigation will not be explicitly allowed.

- **Rescue medication.**

The use of rescue medication required by the patient is contemplated: analgesia, antipyretics, albumin in abundant ascitic losses, ...

- **Compliance evaluation.**

Following the randomization plan, all patients will be evaluated daily during their stay in the ward. All files must be available for review by the Promoter or the Promoter's representative.

- **STUDY VARIABLES.**

The following variables will be collected for each patient:

- **Recipient preoperative** variables: gender, age, pre-transplant stay, BMI, ASA, diabetes, HTN, dialysis, MELD, Child-Pugh, serology, albumin, bilirubin, INR, CRP, creatinine, ascites, SBP, prothrombin time, encephalopathy, time from SSI to HT (months), retransplantation, previous surgeries, cirrhosis etiology, indication for transplantation, sarcopenia.
- **Donor** characteristic variables: age, stay in ICU, vasoactive drugs, cultures, antibiotics, CIT, WIT, type of donation (DBD / DCD), previous immunosuppression.
- **Intraoperative** variables: placement or not of abdominal drainage, surgical time (min), transfusions, blood loss, surgical technique, arterial anastomosis type, biliary anastomosis type, donation with extended criteria, recipient with extended criteria, clamping times.
- **Postoperative** variables: ICU stay, hospital stay, abdominal complications (collection, bile leak, hematoma, hemorrhage, paralytic ileus, ascites, bleeding, wound drainage complications, vascular anastomosis complications, mechanical obstruction, hollow viscus perforations, wound complications surgery), graft function, post-transplant antibiotic therapy, post-transplant immunosuppressive regimen, number of post-HT HC, mortality at 90 days, global complications at 90 days.

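### Modelling all 45 listed pre-closure variables on about 26 expected events would very probably name false risk factors, and would inflate the drain odds ratio if all enter one model

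*Combined protocol and SAP*

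**What the plan says.** The Statistics section gives one sentence on secondary analysis: "The univariate and multivariate study of all the included variables will be carried out". The Descriptive analysis paragraph adds the output: "In this multivariate analysis, the odds ratios will be obtained with a 95% confidence interval". The same paragraph treats any association with p below 0.05 as significant. Nothing states the outcome of the model, which variables are candidates, how they are chosen, how many may enter, or how repeated testing is handled.

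The variables are listed in the Abstract, under Data collect and again under Study variables. The recipient list alone ends with "encephalopathy, time from SSI to HT (months), retransplantation, previous surgeries, cirrhosis etiology, indication for transplantation, sarcopenia". Donor, intraoperative and postoperative lists and the SF-36 domains complete the set.

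The Sample size section supplies the event rates. The complication risk "was assumed to be 9% in the drain group and 6% in the no-drain group", and "the sample was calculated as 174 patients in each arm".

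**The concern.** A logistic model can support only as many terms as its events allow. With far more terms than events, maximum-likelihood odds ratios move away from 1 and their intervals cover too seldom. Separately, testing dozens of variables at p<0.05 without correction will nearly always find something.

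This is the only adjusted analysis that the plan names. Two things are at stake. An adjusted drain odds ratio from an over-filled model could be quoted as the treatment effect; at the assumed risks the exaggeration would favour omitting the drain, which is the direction of the trial's hypothesis. And variables with no real association could be published as independent predictors of complications after transplantation.

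**Working it through.** **1. The plan's own sample size.** The inputs are "was assumed to be 9% in the drain group and 6% in the no-drain group" and "Under a 4% non-inferiority margin, an alpha error of 0.05, and a statistical power of 80"%. With unpooled variance:

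- variance term: 0.09 × 0.91 + 0.06 × 0.94 = 0.0819 + 0.0564 = 0.1383
- distance to the margin: 0.04 + 0.03 = 0.07
- n per arm = 0.1383 × (1.645 + 0.842)² / 0.07² = 174.5

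This agrees with the stated 174 when alpha is one-sided 0.05. For dropout, 348 × 1.05 = 365.4, against a stated 365.

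**2. Expected events.** 174 × (0.09 + 0.06) = 26.1 among 348 evaluable patients. If all 365 are evaluable, 365/2 × 0.15 = 27.4.

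**3. Variables.** Counting the items under Study variables: 26 recipient + 9 donor + 10 intraoperative = 45. One of these is drain placement, which leaves 44 covariates.

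- Events per variable: 26.1/45 = 0.58, or 27.4/45 = 0.61.
- Expanding multi-level factors (ASA, Child-Pugh, etiology, indication, technique) lowers the ratio further.
- Several items overlap: MELD and Child-Pugh stand beside bilirubin, INR, creatinine, albumin, ascites and encephalopathy.
- Postoperative variables are left out of the count. Some of them are components or consequences of the outcome.

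**4. Multiple testing alone.** For 45 independent null variables tested at 0.05, the expected number of false positives is 45 × 0.05 = 2.25. The chance of at least one is 1 − 0.95⁴⁵ = 0.90. This does not depend on the number of events.

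**5. Simulated trials.** Settings: 348 patients, risks of 9% and 6%, 44 covariates unrelated to outcome (half binary), ordinary maximum-likelihood logistic regression. The true drain odds ratio is (0.06/0.94)/(0.09/0.91) = 0.645. Ranges are over separate sets of runs with 400 to 1,500 trials per setting where the number is known.

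| Model | Median drain OR | Coverage of 95% interval | Trials with a false predictor |
|---|---|---|---|
| All 44 covariates plus arm | 0.53 to 0.56 | 89% to 92% | about 95% |
| Screened at p<0.05, then modelled with arm | 0.646 to 0.655 | 94.5% to 96% | 81% to 86% |
| Arm plus 2 or 3 covariates | 0.63 to 0.65 | 95% to 96% | not tabulated |

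In the all-in model the mean drain log odds ratio was inflated by 44% to 52%. An average of 3.7 to 3.8 noise variables reached p<0.05, against 44 × 0.05 = 2.2 expected from valid tests. After screening, 1.5 to 1.7 false predictors remained on average.

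**6. Higher event rates (assumed, not in the documents).** At risks of 30% and 20%, 174 × 0.50 = 87 events, or 87/45 = 1.9 per variable. The all-in inflation falls to about 10% to 20%. At 50% and 40% it was 12% in one set of runs. In these settings more than 90% of all-in fits still named a false predictor.

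**The case against.** The strongest reply is that the text does not say that all variables enter one model. Univariate and multivariate study can equally mean a screen followed by a model, and the Data handling section foresees regrouping variables, so 45 need not be the number of terms. This stands. A reader might infer that the drain effect will be exaggerated however the plan is carried out. The documents do not support that, because under screening the drain odds ratio is about unbiased. What survives under both readings is the false predictors.

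A reader might also blame those false predictors on the small number of events. Step 4 shows that they come mainly from uncorrected testing; few events add to the problem.

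The figure of 26 events is itself uncertain. The assumed risks describe early complications related to the transplant, whereas the endpoint is Clavien-Dindo complications over 90 days with no grade cut-off, and grade I is broad. More events would reduce the inflation but would not remove the false predictors. In addition, postoperative stay and SF-36 scores are quantitative, so event counts do not apply to models of them. The promise of odds ratios implies a binary model but does not say for which outcome.

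Routine non-convergence is a further tempting inference. Simulated rates of failed or separated fits ran from 1.5% to 14%, depending on covariate prevalence and convergence criterion, so no weight is placed on them.

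Finally, this is a secondary analysis. Nothing makes it primary or confirmatory, and it does not undermine the unadjusted comparison of incidence between arms.

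**Conclusion.** The concern holds for the secondary multivariable analysis. At the plan's own rates there are about 26 events for 45 listed pre-closure variables.

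- **All variables in one model:** the drain log odds ratio is inflated by about 45% to 50%, coverage is roughly 91%, and about 95% of fits name at least one noise variable.
- **Univariate screen first:** the drain odds ratio is about unbiased, but about 80% to 86% of trials still report a false independent predictor.

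The counts follow directly from the documents. The simulated sizes assume independent, unrelated covariates and the 9% and 6% risks, and they shift with covariate mix and Monte Carlo error. The direction of the inflation does not. This is more than missing detail, because the stated rule misleads if it is followed. It should be corrected, but it is no reason to doubt the non-inferiority comparison itself.

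**What to change.** Replace the sentence under Secondary variables analysis with:

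> *The multivariable model for 90-day complications contains the randomised arm and a small number of pre-randomisation covariates named in advance (about two or three at the planned event count, for example MELD in place of its components). Any other risk-factor analysis is exploratory, is labelled so, and carries no significance claims.*

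Penalised (Firth) regression is optional, since ordinary maximum likelihood performs adequately at this model size. The covariates should be named before outcome data are analysed. The cost is one sentence, and the broad risk-factor model becomes an exploratory description.
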